45 zeros were observed. Given this heterogeneity assumption, a Bayesian hierarchical  
46 random-effects model was used to analyze the data. The assumption of our model  
47 was that the number of individuals  $y_j$  responding to influenza vaccination is  
48 binomially distributed as:

49  $y_j \sim \text{Binomial}(p_j, n_j)$ ,

50 where the success rate ( $p_j$ ) was the probability of influenza onset in mothers and  $n_j$   
51 was the number of individuals in the  $j$ th group. We note that there are only 2 groups  
52 ( $j=1,2$ ): the vaccinated and the not vaccinated groups. The probability ( $p_j$ ) itself  
53 follows a beta distribution with parameters ( $a_j, b_j$ ). Non-informative distributions  
54 priors distributions were placed on the parameters of the beta distributions. P-values  
55 of 0.05 or less were considered statistically significant. IVE against influenza was  
56 estimated as follows:  $[1 - (\text{incidence rate of influenza in vaccinated women} / \text{incidence rate of influenza in unvaccinated women})] \times 100$  [11]. The statistical analysis was  
57 conducted using R 3.6 (R Foundation for Statistical Computing).  
58

59

60

61 **Results**

62 A total of 949 pregnant women were enrolled in the study (Figure 1). Of them, 94  
63 women were excluded from the analysis because of the following reasons: lost to  
64 follow-up or decision to withdraw from the study (65 women), post-partum influenza  
65 vaccination (cocooning) (25 women), spontaneous abortion (3 women), and perinatal  
66 death (1 woman). Therefore, 855 pregnant women were included in the analysis.  
67 Their mean age was 32.9 years (range: 18-45 years) and their mean gestational age at  
68 enrollment was 23.3 weeks (range: 3-39 weeks).

69 Of the 855 pregnant women, 525 (61.4%) were vaccinated against influenza and 330  
70 (38.6%) refused vaccination. No serious adverse event occurred. Pregnant women  
71 with a history of influenza vaccination the past (2018-2019) season were more likely  
72 to get vaccinated against influenza in 2019-2020 compared to women with no history  
73 of vaccination (91.8% versus 55.1%, p-value<0.001). In the logistic regression  
74 analysis the following variables were significantly associated with a history of  
75 influenza vaccination in 2019-2020: lower gestational age (OR: 0.998; CI: 0.998-  
76 0.999), influenza vaccination the past season (OR: 8.8; CI: 4.7-16.2), and no smoking  

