77 during pregnancy (OR: 0.6; CI: 0.4-0.9).

78 ***Estimation of IVE in pregnant women***

79 Of the 855 pregnant women included in the analysis, 636 women were still pregnant  
80 during the 2019-2020 influenza season and comprised the study group for the  
81 estimation of IVE in pregnancy. Of them, 406 women (63.8%) were vaccinated  
82 against influenza and 230 (36.2%) refused vaccination. Table 1 shows their  
83 characteristics by influenza vaccination status.

84 Twelve of the 636 pregnant women tested positive for influenza (8 cases of influenza  
85 A/H3N2, 2 cases of A/H1N1 and 2 cases of influenza B). Table 2 summarizes their  
86 morbidity by influenza vaccination status. The incidence of influenza differed  
87 between vaccinated women (6/406; 1.47%) and unvaccinated women (6/230; 2.6%),  
88 however the difference was not statistically significant. Similarly, higher rates of  
89 febrile episode, ILI, pneumonia, healthcare seeking, hospitalization, use of antibiotics  
90 and antivirals were noted in the unvaccinated group compared to the vaccinated  
91 group, however none of these differences reached statistical significance (Table 2).  
92 The IVE of QIV against influenza was 43.5% for pregnant women during 2019-2020  
93 in Greece. The IVE of QIV against influenza was 43.5% (95% CI: 28.4%-55.6%) for  
94 pregnant women during 2019-2020 in Greece.

95 According to the regression model the age was not a predictor of influenza onset in  
96 the sample of pregnant women. Influenza vaccination of pregnant women reduced  
97 their logit to develop influenza by -4.2 (95% CI -3,7 -4,7), which indicates that  
98 influenza vaccination added a statistically significant protection to pregnant women.

99 ***Estimation of IVE in infants***

100 A total of 474 infants were born before or during the 2019-2020 influenza season and  
101 constituted the group for the estimation of IVE in infants. Their mean birth weight  
102 was 3189 g (range: 630-4650 g) and their mean gestational age was 39.1 weeks  
103 (range: 28-42 weeks). There were 281 (59.3%) infants whose mothers were  
104 vaccinated during pregnancy and 193 (40.7%) infants of unvaccinated mothers. The  
105 unvaccinated mothers had a mean gestational age of 31.2 weeks at enrollment  
106 compared to a mean gestational age of 28.3 weeks of vaccinated mothers (p-value

107 <0.001); no other significant difference was noted between the two groups (data not  
108 shown).

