109 Overall, 8 of the 474 infants tested positive for influenza (5 cases of influenza  
110 A/H3N2, 2 cases of influenza A/H1N1 and 1 of influenza B). Table 3 summarizes  
111 their morbidity by maternal influenza vaccination status. Infants of unvaccinated  
112 mothers more often developed influenza, febrile episodes, ILI, ARI, AOM and  
113 pneumonia and had increased rates of healthcare seeking, hospitalization, use of  
114 antibiotics and use of antiviral agents compared to infants whose mothers were  
115 vaccinated, however these differences reached statistical significance only for ARI  
116 and use of antiviral agents (p-values=0.012 and 0.036, respectively). The IVE against  
117 influenza for infants was estimated at 31.4% in 2019-2020. The IVE against influenza  
118 for infants was estimated at 31.4% (95% CI: 4%-51%) in 2019-2020.

119 According to the regression model the age of pregnant women was not a predictor of  
120 influenza onset in the sample of young infants. Additionally the influenza vaccination  
121 of pregnant women reduced the logit of their infants to develop influenza by -4.2  
122 (95% CI -3.6, -4.9), which indicates that influenza vaccination during pregnancy  
123 added a statistically significant protection to young infants.

124

125

126

127

128

129 **Table 1. Characteristics of pregnant women (n=636) by influenza vaccination status**130 **Characteristic** **Vaccinated** **Unvaccinated** **P-value**131 **n=406 (%)** **n=230 (%)**

132 \_\_\_\_\_

133 Mean age, years (range) 33.1 (21-45) 32.3 (18-45) 0.055

134 Mean gestational age, weeks (range) 19.3 (3-39) 21.6 (3-39) 0.003

135 Underlying disease 49 (12.2) 32 (14.0) 0.512

136 Influenza vaccination the past season 94 (23.2) 14 (6.1) <0.001

137 Mean no. of cohabitants (range) 1.7 (0-8) 1.8 (0-8) 0.147

138 Children <5 years 161 (39.8) 79 (34.5) 0.190

139 Mean no. of children <5 years (range) 0.5 (0-3) 0.4 (0-3) 0.325

140 No smoking during pregnancy 350 (93.1) 173 (84.0) 0.001

141 142 Smoking during pregnancy 26 (6.9) 33 (16.0)

143 \_\_\_\_\_

144

145

146

147

148

149

150

151 **Table 2. Morbidity (%) of pregnant women (n=636) by influenza vaccination status**

152	Type of morbidity	Vaccinated	Unvaccinated	P-value
153		n = 406 (%)	n = 230 (%)	
154	Influenza*	6 (1.5)	6 (2.6)	0.314
155	Febrile episode	17 (4.2)	13 (5.7)	0.402
156	ARI	115 (28.3)	50 (21.7)	0.069
157	ILI	11 (2.7)	11 (4.8)	0.169
158	Pneumonia	2 (0.5)	4 (1.7)	0.118

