159	Healthcare seeking	5 (1.2)	5 (2.2)	0.359
160	Hospitalization	0 (0.0)	1 (0.4)	0.184
161	Use of antibiotics	11 (2.7)	7 (3.0)	0.807
162	Use of antivirals	3 (0.7)	4 (1.7)	0.245

163

164 \* laboratory-confirmed influenza

165 ARI: acute respiratory infection; ILI: influenza-like illness

166

167

168

169

170 **Table 3. Morbidity (%) of infants (n=474) by maternal influenza vaccination status**

171	Type of morbidity	Vaccinated	Unvaccinated	P-value
172		n = 281 (%)	n = 193 (%)	
173	Influenza*	4 (1.4)	4 (2.1)	0.59
174	Febrile episode	7 (2.5)	8 (4.1)	0.312
175	ARI	17 (6.0)	27 (14.0)	0.012
176	ILI	6 (2.1)	6 (3.1)	0.507
177	AOM	1 (0.3)	2 (1.0)	0.358
178	Pneumonia	0 (0.0)	1 (0.5)	0.227
179	Healthcare seeking	6 (2.1)	10 (5.2)	0.144
180	Hospitalization	0 (0.0)	1 (0.5)	0.277
181	Use of antibiotics	4 (1.4)	5 (2.6)	0.360
182	Use of antivirals	0 (0.0)	3 (1.6)	0.036

183

184 \* laboratory-confirmed influenza

185 ARI: acute respiratory infection; ILI: influenza-like illness; AOM: acute otitis media

186

187

188

189

190

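### The intervals printed as 95% around the logit of -4.2 are too narrow for 95% on the SAP's own counts, in mothers and in infants, and they cannot support a vaccine effect

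*SAP*

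**What the plan says.** Under *Estimation of IVE in pregnant women*, the SAP reports that vaccination reduced "their logit to develop influenza by -4.2 (95% CI -3,7 -4,7), which indicates that" vaccination protected pregnant women to a statistically significant degree. Under *Estimation of IVE in infants*, it reports that maternal vaccination "of pregnant women reduced the logit of their infants to develop influenza by -4.2", with "95% CI -3.6, -4.9), which indicates that influenza vaccination during pregnancy" gave significant protection to infants. Both sentences are worded as a difference due to vaccination, and both intervals carry a 95% label.

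The counts behind them are also printed. For mothers the comparison is "between vaccinated women (6/406; 1.47%) and unvaccinated women (6/230; 2.6"%, with p = 0.314 in Table 2. For infants, Table 3 has the row "Influenza* 4 (1.4) 4 (2.1) 0.59". Its denominators are in the text: "There were 281 (59.3%) infants whose mothers were" "vaccinated during pregnancy and 193 (40.7%) infants of unvaccinated mothers".

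The *Statistical analysis* section describes a beta-binomial model with one probability per vaccination group, where n_j "was the number of individuals in the $j$ th group. We note that there are only 2 groups". Priors are non-informative. The same section also mentions logistic regression with a random intercept, Bayesian model selection and a hierarchical random-effects model. It sets significance at 0.05.

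**The concern.** With 6 and 4 events in the vaccinated groups, a logit cannot be estimated as precisely as the printed half-widths (0.50 and 0.65) imply, unless information enters from elsewhere. Non-informative priors supply none.

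The regression claims of significant protection, including the one for the primary outcome, rest on these two intervals. The same document's direct comparisons give p = 0.314 and p = 0.59. A reader who trusts the 95% label will take the Bayesian analysis to have found an effect that the plain comparison missed.

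**Working it through.** **Inputs.** Mothers: 6/406 vaccinated, 6/230 unvaccinated (text and Table 2). Infants: 4/281 and 4/193 (text and Table 3). Printed intervals: mothers -4.7 to -3.7, infants -4.9 to -3.6.

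**1. Reproduce the point estimate.** The logit of a group's own proportion is ln(y/(n - y)).
- Mothers, vaccinated: ln(6/400) = -4.20.
- Infants, vaccinated mothers: ln(4/277) = -4.24.

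Both round to the printed -4.2.

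**2. Try to reproduce the intervals on that reading.** SE = sqrt(1/y + 1/(n - y)).
- Mothers: sqrt(1/6 + 1/400) = 0.411.
- Infants: sqrt(1/4 + 1/277) = 0.504.

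| | Printed | 80% limits (±1.28 SE) | 95% limits (±1.96 SE) |
|---|---|---|---|
| Mothers | -4.7 to -3.7 | -4.73 to -3.67 | -5.01 to -3.39 |
| Infants | -4.9 to -3.6 | -4.88 to -3.59 | -5.22 to -3.25 |

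The 80% limits round to all four printed bounds and the 95% limits to none. The printed half-widths are 0.50/0.411 = 1.22 SE and 0.65/0.504 = 1.29 SE. They correspond to coverage of 77.6% (73% to 82% if the half-width moves by 0.05 for rounding) and 80.3% (77% to 84%).

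**3. Replace the Wald formula by a beta posterior.** Under near-Haldane, Jeffreys and uniform priors, the posterior mass inside the printed interval is 0.77 to 0.78 for mothers and 0.79 to 0.81 for infants. The Jeffreys 10th to 90th percentiles are -4.74 to -3.69 and -4.89 to -3.63, which again round to the four printed bounds; the other two priors do not match every bound. The Jeffreys 95% intervals are -5.08 to -3.47 and -5.33 to -3.36.

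**4. Take the sentences literally, as a contrast.** The log odds ratio is the difference of the two group logits, with SE = sqrt(sum of the four reciprocal cell counts).
- Mothers: -4.20 - (-3.62) = -0.58, SE 0.583, 95% CI -1.72 to 0.56.
- Infants: -4.24 - (-3.86) = -0.38, SE 0.713, 95% CI -1.78 to 1.02.

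Neither centre is near -4.2. On these SEs the printed half-widths would cover about 61% (0.50/0.583 = 0.86 SE) and 64% (0.65/0.713 = 0.91 SE). They would have to be 2.3 and 2.2 times as wide. An uncorrected chi-squared test on the same counts gives p = 0.314 and p = 0.590, in agreement with Tables 2 and 3.

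**5. Other readings at 95%.**
- Pooled over both groups: 12/636 gives -3.95 (-4.52 to -3.38); 8/474 gives -4.06 (-4.76 to -3.37).
- Unvaccinated group: -3.62 (-4.43 to -2.81) and -3.86 (-4.85 to -2.87).

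Neither matches the printed centre and bounds. Using every maternal event in one logit, the 95% half-width is still 0.57, above the printed 0.50 and above 0.55 with rounding. For infants it is 0.70, reached only at the extreme of rounding and around a different centre.

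**The case against.** The strongest objection is that the fitted model is not shown. The SAP mentions a random intercept, model selection and hierarchical effects. Such a model could draw on all 12 or all 8 events, and a random intercept moves the conditional intercept further from zero. With a pooled intercept, a flat prior and an assumed random-intercept SD of 0.5 to 0.7, the posterior means are about -4.11 to -4.23 (mothers) and -4.25 to -4.36 (infants). The printed intervals then hold about 89% to 91% and 91% to 92% of the posterior. This stands in part: the implied coverage depends on the model, so 80% cannot be stated as a fact whatever -4.2 means. It does not rescue the label, because this reading also falls short of 95%. A pooled intercept would also say nothing about vaccination.

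Three stronger readings are tempting, and the SAP does not support them.
- *The 10th to 90th percentiles were extracted by mistake.* The match of all four bounds makes this likely, but the model output is not given.
- *Every interval in the results has the same fault.* The SAP does not link the IVE intervals to this model run. That is a reason to check them, not a finding.
- *Widening the intervals settles the matter.* It does not. A logit of zero is a risk of 50%, so any reasonable interval for the risk of a rare disease excludes zero. Limits of -5.0 to -3.4 would leave the significance claim looking intact.

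**Conclusion.** The point holds: the 95% label and the printed widths do not agree in either population, and no reading tested reproduces both intervals at 95%.

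The size depends on what -4.2 is. As the vaccinated group's own logit, which the counts support, the printed intervals behave like 80% intervals, and 95% intervals would be about 1.6 (mothers) and 1.5 (infants) times as wide. On the risk scale, mothers go from 0.9%-2.4% to 0.7%-3.3%, and infants from 0.7%-2.7% to 0.5%-3.7%. As a contrast, which the wording asserts, the figure itself is wrong as well as its interval.

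On either reading the claim of significant protection has no support here. The between-group intervals computed from the counts include zero in both populations, in line with p = 0.314 and p = 0.59. These figures assume simple binomial counts without covariates; the fitted model's own contrast may differ somewhat.

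**What to change.** - Report the vaccinated-versus-unvaccinated contrast from the fitted model, with its 2.5th to 97.5th posterior percentiles, for mothers and for infants. Withdraw the claim of significant protection in each population where that interval includes zero, as the counts indicate for both.
- If -4.2 is kept, call it the logit of influenza risk in the vaccinated group. Give its 95% posterior interval taken from the model, not the approximate limits above. Do not cite it as evidence of a vaccine effect.
- State which coefficient and which percentiles each reported interval uses, and check the interval level of any other output from the same run.

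The work is to re-extract summaries from the existing model output and rewrite two sentences; no new data are needed. The price is wider intervals and a weaker conclusion.

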1    **Official Title**

2    **Influenza Vaccination Effectiveness of a Quadrivalent Inactivated Vaccine in**  
3    **Pregnant Women and Young Infants (Aged 6 months and Below) During**  
4    **Influenza Season 2019-2020**

5

6    **Unique Protocol ID: 16708**

7    **6 May 2021**

8

9

10

11

12

13

14

15

16

17

18

19

20 **Statistical analysis**

21 Women were excluded from the statistical analysis for the following reasons that  
22 occurred before the onset of influenza season: decision to withdraw from the study,  
23 loss to follow-up, post-partum influenza vaccination (cocooning), pregnancy  
24 discontinuation, spontaneous abortion, perinatal death. Women were followed for the  
25 entire influenza season, regardless of onset of influenza or ILI. The analysis was  
26 restricted to the influenza season. The primary outcome of the study was influenza  
27 onset in pregnant women. Secondary outcomes were the onset of influenza in their  
28 infants and the onset of ILI, ARI, febrile episode, pneumonia, healthcare seeking,  
29 hospitalization, use antibiotics and use of antivirals in pregnant women and their  
30 infants. Categorical and continuous variables were compared between vaccinated and  
31 unvaccinated groups using the  $\chi^2$  test and T-test, respectively. Logistic regression  
32 analysis was conducted in order to identify factors significantly associated with a  
33 history of influenza vaccination in 2019-2020. Odds ratio (OR) and confidence  
34 intervals (CIs) were estimated. We have used a Bayesian model selection for logistic  
35 regression models with random intercept. The primary outcome of interest was to  
36 estimate the average rate of influenza for each group (vaccinated versus unvaccinated  
37 group). Our data was a 2 by 2 cross-tabulated data arising from two binary variables  
38 with possible values 0 or 1. The first variable was whether a pregnant woman has  
39 been vaccinated (value =1) or not (value =0). The second variable was the age group  
40 of the pregnant woman. The first group consisted of pregnant women aged less than  
41 32 years (value =0) or not (value=1). We compared the vaccinated pregnant women  
42 group with the group of non-vaccinated pregnant women to model the proportion of  
43 effectiveness that is the event that a pregnant woman had influenza. We used the  
44 Bayesian beta-binomial model due to data heterogeneity because of a large number of

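### The infant vaccine effectiveness of 31.4% compares head counts, not time at risk, although infants entered before or during the season and birth timing may differ by group

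*SAP*

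**What the plan says.** In the SAP, the Statistical analysis section says the analysis was "restricted to the influenza season". It gives one effectiveness formula, worded for women only: one minus the ratio of the "incidence rate of influenza in vaccinated women" to the same quantity in unvaccinated women. The model in that section is binomial, with the number of individuals per group as its denominator. No person-time or offset is described.

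Under Estimation of IVE in infants, the analysis set is defined by "A total of 474 infants were born before or during the 2019-2020 influenza season and", and the result is that effectiveness against "influenza for infants was estimated at 31.4% in 2019-2020". Table 3 gives 4 cases among 281 infants of vaccinated mothers and 4 among 193 infants of unvaccinated mothers. Maternal age is the only other covariate named for the infant model. The title limits the infant population to "Young Infants (Aged 6 months and Below" in age.

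The same section reports that "unvaccinated mothers had a mean gestational age of 31.2 weeks at enrollment", "compared to a mean gestational age of 28.3 weeks of vaccinated mothers" (p < 0.001). It reports no other significant difference between the infant groups.

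**The concern.** A ratio of proportions is a fair summary when everyone is at risk for about the same time. Here entry is staggered by design. An infant born before the season can be at risk for all of it; one born near its end is at risk for very little. Follow-up for the whole season is stated for women only, and an infant born mid-season could not have it.

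If the two groups differ in when their infants were born, the head-count ratio mixes any vaccine effect with a difference in exposure time. With four cases in each group the estimate is just one minus the ratio of the denominators, so any change in the denominators passes straight into it. The same denominators underlie every contrast in Table 3. The SAP presents the infant result as statistically significant protection, with no caveat about exposure.

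**Working it through.** **1. Reproducing the stated figure.** Inputs from Table 3: 4/281 and 4/193.

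- Ratio = (4/281)/(4/193) = 193/281 = 0.687, so effectiveness = 31.3%.
- With percentages rounded to two decimals: 1 - 1.42/2.07 = 31.4%, the printed value.

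The estimate is therefore a head-count ratio.

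**2. Does birth timing differ by group?** The SAP Results give 525 vaccinated and 330 unvaccinated women, of whom 406 and 230 were still pregnant in the season.

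- No longer pregnant: 525 - 406 = 119 (22.7%) and 330 - 230 = 100 (30.3%). Check: 119 + 100 = 219 = 855 - 636.
- Pearson chi-square 6.20, p = 0.013.
- The gestational ages at enrollment (28.3 and 31.2 weeks, a gap of 2.9 weeks) point the same way. The two comparisons overlap and are not independent.

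If each of those 219 women contributed one infant, which the SAP does not state, pre-season births were 119/281 = 42.3% (vaccinated) and 100/193 = 51.8% (unvaccinated). That contrast is borderline: p = 0.042 uncorrected, 0.053 with continuity correction, 0.049 by Fisher's test. With three fewer pre-season infants in each group (116/281 and 97/193), p = 0.054 and Fisher 0.060.

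**3. Effect on the estimate (illustrations).** Assume singletons, one infant per woman and constant risk over the season. Let g be the share of the season at risk for infants born before it, and f the share for those born during it. In-season births number 281 - 119 = 162 and 193 - 100 = 93.

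- Exposure, vaccinated: Ev = 119g + 162f.
- Exposure, unvaccinated: Eu = 100g + 93f.
- With 4 cases in each group, rate ratio = (4/Ev)/(4/Eu) = Eu/Ev.

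| g | f (vaccinated) | f (unvaccinated) | Eu/Ev | Effectiveness |
|---|---|---|---|---|
| 1 | 0.25 | 0.25 | 123.25/159.5 = 0.773 | 23% |
| 1 | 0.5 | 0.5 | 146.5/200 = 0.7325 | 27% |
| 1 | 0.75 | 0.75 | 169.75/240.5 = 0.706 | 29% |
| 0.75 | 0.75 | 0.75 | 144.75/210.75 = 0.687 | 31% |
| 0.5 | 0.5 | 0.5 | 96.5/140.5 = 0.687 | 31% |
| 0.6 | 0.75 | 0.75 | 129.75/192.9 = 0.673 | 33% |
| 0.5 | 0.75 | 0.75 | 119.75/181 = 0.662 | 34% |
| 1 | 0.5 | 0.6 | 155.8/200 = 0.779 | 22% |
| 1 | 0.6 | 0.5 | 146.5/216.2 = 0.678 | 32% |

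Rows with g below 1 represent pre-season infants passing 6 months of age before the season ends. That can remove the shift or reverse it.

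**4. Sampling error for comparison.** The log standard error of the head-count ratio is sqrt(1/4 - 1/281 + 1/4 - 1/193) = 0.701. The 95% interval for effectiveness is then about -171% to 83%. The exact conditional interval (4 of 8 cases, head counts as exposure) is about -269% to 87%.

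**5. Other Table 3 outcomes.** For ARI the rate ratio is (17/Ev)/(27/Eu), with log standard error sqrt(1/17 + 1/27) = 0.310. Over the equal-f rows it runs from 0.417 (0.23 to 0.76) to 0.487 (0.27 to 0.89), against 0.43 by head count, so ARI stays significant. The antiviral contrast (0/281 versus 3/193) is fragile whatever the time at risk: uncorrected p = 0.036 as printed, Fisher p = 0.067.

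**The case against.** The strongest case on the other side has four parts.

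- **The estimator is recognised and visible.** The document also calls 6/406 in women an incidence, so its usage is consistent, and a reader can see that Table 3 shows cases over infants. This stands: there is no contradiction in terms. But attack proportions suit equal exposure, which staggered entry rules out for individual infants and which is not shown to balance between groups.
- **The timing difference is inferred.** Gestational age at enrollment fixes birth timing only if the groups enrolled at similar calendar times, and the infant-level contrast needs one infant per woman. It is sensitive to that: lowering only the unvaccinated count by five (119/281 versus 95/193) gives p = 0.14, while lowering only the vaccinated count by five (114/281 versus 100/193) gives p = 0.016. This also stands. The comparison of women no longer pregnant does not depend on enrollment dates, however.
- **No conclusion changes.** Influenza in infants is already non-significant in Table 3 (p = 0.59), and ARI stays significant in the equal-f scenarios. This is correct and limits the weight of the point; it does not make the estimator unbiased.
- **Dates and the infant follow-up window may be in the protocol.** Their absence from the SAP is not held against it here. It only means that the bias cannot be quantified from this document.

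**Conclusion.** The point holds as a modest one. The 31.4% is a ratio of attack proportions in a group with staggered entry, with no described adjustment for time at risk, and the document's own counts suggest that more unvaccinated than vaccinated women delivered before the season. That excess makes bias in the vaccine's favour the more plausible direction, but ageing out at 6 months or group differences in birth dates within the season could cancel or reverse it.

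The illustrations put the adjusted estimate between 22% and 34%. They rest on singletons, one infant per woman no longer pregnant, constant risk and assumed exposure fractions; none of these can be checked from the SAP. The shift is small beside the sampling error of 8 cases. What is lost is interpretability: a reader cannot tell how much of 31.4% reflects exposure time.

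**What to change.** From birth dates, compute infant-weeks at risk for each infant, from the later of birth and season start to the earliest of the event, 6 months of age or season end. Report infant effectiveness as one minus the rate ratio, with an exact interval for influenza, and give rate ratios for the other Table 3 outcomes. Where event dates are missing, stratify by birth before versus during the season. If neither is possible, label 31.4% as a ratio of attack proportions not adjusted for time at risk, and do not assert a direction of bias.

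The cost is low. Birth timing relative to the season was already needed to define the 474 infants and the 636 women, so the stratified version should be feasible. Person-time also needs event dates, which the document does not show were recorded. With 8 cases the strata will be sparse, the interval will stay very wide, and the estimate may come out a few points less favourable.

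### Three p-values in Table 3 (infant ARI, healthcare seeking, hospitalization) do not follow from the counts printed beside them

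*SAP*

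**What the plan says.** The Statistical analysis section names the test: "Categorical and continuous variables were compared between vaccinated and" unvaccinated groups with the chi-square "test and T-test, respectively". It mentions no continuity correction or exact test. The significance rule is that p-values "of 0.05 or less were considered statistically significant".

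The infant denominators are in the Results section on IVE in infants: "There were 281 (59.3%) infants whose mothers were" "vaccinated during pregnancy and 193 (40.7%) infants of unvaccinated mothers". The same section says of the infant outcomes that those of unvaccinated mothers fared worse than those whose mothers were "vaccinated, however these differences reached statistical significance only for ARI" "and use of antiviral agents (p-values=0.012 and 0.036, respectively").

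The Table 3 rows at issue, with pneumonia for comparison:

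| Outcome | Vaccinated, n = 281 | Unvaccinated, n = 193 | Printed p |
|---|---|---|---|
| ARI | 17 (6.0%) | 27 (14.0%) | 0.012 |
| Healthcare seeking | 6 (2.1%) | 10 (5.2%) | 0.144 |
| Hospitalization | 0 (0.0%) | 1 (0.5%) | 0.277 |
| Pneumonia | 0 (0.0%) | 1 (0.5%) | 0.227 |

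**The concern.** Pneumonia and hospitalization show the same 2×2 table with two different p-values, which cannot happen under one test. That prompted a recalculation of every row in Tables 2 and 3.

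ARI matters most. It is one of only two infant outcomes called significant, and the other, antiviral use, rests on three events. If the ARI counts are wrong, so is the reported contrast of 6.0% against 14.0%. If the p-value is wrong, the error sits in both the table and the text. If another test was used, the reader has not been told.

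**Working it through.** **Inputs.** Counts and p-values from Tables 2 and 3; denominators 406 and 230 (women), 281 and 193 (infants).

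**Formula.** With a of n₁ vaccinated and c of n₀ unvaccinated having the event, b = n₁ − a, d = n₀ − c, N = n₁ + n₀ and e = a + c, the uncorrected Pearson statistic is X² = N(ad − bc)² / [n₁ n₀ e (N − e)], on 1 df.

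**Step 1: identify the test from the other rows.**

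| Row | Computed p | Printed p |
|---|---|---|
| Women: influenza | 0.3139 | 0.314 |
| Women: febrile episode | 0.4024 | 0.402 |
| Women: ARI | 0.0687 | 0.069 |
| Women: ILI | 0.1692 | 0.169 |
| Women: pneumonia | 0.1182 | 0.118 |
| Women: healthcare seeking | 0.3587 | 0.359 |
| Women: hospitalization | 0.1836 | 0.184 |
| Women: antibiotics | 0.8071 | 0.807 |
| Women: antivirals | 0.2454 | 0.245 |
| Infants: influenza | 0.5899 | 0.59 |
| Infants: febrile episode | 0.3122 | 0.312 |
| Infants: ILI | 0.5074 | 0.507 |
| Infants: AOM | 0.3588 | 0.358 |
| Infants: pneumonia | 0.2271 | 0.227 |
| Infants: antibiotics | 0.3603 | 0.360 |
| Infants: antivirals | 0.0360 | 0.036 |

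All nine rows for women and seven of ten for infants agree; AOM looks truncated instead of rounded. So the test in use was the uncorrected two-level Pearson chi-square.

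**Step 2: apply it to the three remaining rows** (N = 474, n₁n₀ = 281 × 193 = 54,233).

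- ARI: ad − bc = 17 × 166 − 264 × 27 = −4,306. X² = 474 × 4,306² / (54,233 × 44 × 430) = 8.565, p = 0.0034. Printed 0.012, a ratio of 0.012/0.0034 = 3.5.
- Healthcare seeking: ad − bc = 6 × 183 − 275 × 10 = −1,652. X² = 474 × 1,652² / (54,233 × 16 × 458) = 3.255, p = 0.0712. Printed 0.144, a ratio of 2.0.
- Hospitalization: ad − bc = 0 × 192 − 281 × 1 = −281. X² = 474 × 281² / (54,233 × 1 × 473) = 1.459, p = 0.2271. Printed 0.277.

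**Step 3: try other common tests.**

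| Row | Printed | Pearson | Yates | Fisher | Likelihood ratio |
|---|---|---|---|---|---|
| ARI | 0.012 | 0.0034 | 0.0057 | 0.0056 | 0.0038 |
| Healthcare seeking | 0.144 | 0.071 | 0.122 | 0.118 | 0.074 |
| Hospitalization | 0.277 | 0.227 | 0.850 | 0.407 | 0.180 |

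None gives the printed value. One-sided, mid-p, Wald and t-test versions fail as well.

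**Step 4: try missing data.** Let each printed percentage be off by 0.1, since AOM 1/281 = 0.356% is printed as 0.3. ARI then allows denominators of 279–281 and 192–193, giving p from 0.0032 to 0.0037. Healthcare seeking allows 273–281 and 189–193, giving 0.064 to 0.081. Neither reaches the printed figure. Hospitalization would reach 0.277 with 228 vaccinated infants in place of 281, but Table 3 reports no such loss.

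**Step 5: try a small miscount.** Keeping 281 and 193, the nearest counts that give 0.012 for ARI are 23 against 30, a shift of 6 + 3 = 9 infants. The nearest that give 0.144 for healthcare seeking are 15 against 5, a shift of 9 + 5 = 14. No pair up to 59 against 59 gives 0.277.

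**Step 6: try a hidden third level.** Splitting the events into two categories and testing on 2 df gives 0.012 for 18 of 502 possible ARI splits and 0.144 for 4 of 75 healthcare-seeking splits (9 and 2 distinct splits once swapped labels are counted once). For example, 1 of the 17 and 3 of the 27 ARI infants in an extra category gives 0.0117. This route is possible for those two rows but not for hospitalization, because one infant cannot fill two event categories.

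**The case against.** The best defence concerns ARI and healthcare seeking. The SAP prescribes a chi-square for categorical variables and does not restrict it to two levels. If those outcomes were recorded in three levels, for instance with repeat episodes, a chi-square on 2 df could give the printed values, as step 6 shows. This keeps the cause open: the two rows are not reproducible from what is printed, but their p-values are not proven wrong. It does not remove the problem. Table 3 prints one count per group, no third level is mentioned, and the same two outcomes in women follow the two-level test to the printed digit (0.069 and 0.359).

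The printed percentages also agree with the counts (17/281 = 6.0%, 27/193 = 14.0%, 6/281 = 2.1%, 10/193 = 5.2%), and step 5 shows that a small miscount will not do. That makes the p-values the more doubtful cells. It does not settle the matter, because percentages calculated from a wrong count would agree with it.

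For hospitalization, 0.277 against 0.227 is one digit and may be a slip. A misreading of that cell when the PDF was converted cannot be wholly excluded. For ARI that explanation is unlikely, because 0.012 appears in the table and again in the text.

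Finally, no inference changes. ARI remains significant, and more strongly so; the other two remain non-significant. The statement of which infant outcomes reached significance stands on the printed counts, and no IVE estimate uses these p-values. That is correct and fixes the weight of the point.

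**Conclusion.** The point holds as a minor reporting error. Under the uncorrected two-level chi-square that the other 16 rows of Tables 2 and 3 follow, the printed counts give 0.0034, 0.071 and 0.227 for ARI, healthcare seeking and hospitalization, against printed values of 0.012, 0.144 and 0.277. The hospitalization row contradicts the pneumonia row of the same table. The other two cannot be reproduced from the printed information, and their cause is unknown.

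This assumes that the counts and denominators are as printed and that each outcome is a yes/no variable. On those terms no call at 0.05 changes. If a count should prove wrong, the rates in that row would need correcting too, and its significance would have to be looked at again.

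**What to change.** Check the counts and p-values of the three rows against the source data and correct whichever figure is wrong. If the counts stand and the two-level chi-square was used, print 0.003 for ARI in Table 3 and in the Results text, 0.071 for healthcare seeking and 0.227 for hospitalization. If a different test or more than two levels was used for a row, say so in a footnote to Table 3 and name the levels.

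The cost is a check of three rows, then either a few table cells and one figure in the text, or one footnote. No re-analysis is needed.
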